#### 6.1.9. Corticosteroid Dose Derivation for Efficacy Analyses

At screening, subjects will be prescribed required initial doses of oral corticosteroid (prednisone or prednisolone) at 0.5 mg/kg/day for newly diagnosed patients (diagnosed  $\leq 6$  months prior to Screening) with PDAI total activity score of  $\geq 15$ , and 0.2 mg/kg/day for relapsing, chronic patients (diagnosed  $> 6$  months prior to Screening) with a PDAI total activity score of  $\geq 9$ . Up-titration of CS during the screening period will be permitted if the starting dose had been insufficient to prevent worsening disease. During the treatment period, CS will be tapered once the subject reached End of Consolidated Phase (ECP) towards a goal of  $\leq 5$  mg/day by  $\leq$  Week 29. Once the 5 mg level is achieved, it will be kept at that level until the time of the primary endpoint at Week 37 is assessed. From Week 37, further tapering to 0 mg CS will be attempted in patients with CR unless medically contraindicated. Up-titration of CS will also be permitted during the treatment period in cases of worsening disease. Further details of the corticosteroid management plan can be found in Appendix 1 of the protocol.

#### 6.1.10. GTI Scores

The Glucocorticoid Toxicity Index is a proprietary licensed instrument from Massachusetts General Hospital (Miloslavsky 2017). It was developed to assess glucocorticoid (GC)-related morbidity and GC-sparing ability of other therapies.

The GTI is composed of two components, the Composite GTI and the Specific List. The Composite GTI consists of nine domains (body mass index (BMI), glucose tolerance, blood pressure, lipid, bone mineral density, glucocorticoid-induced myopathy, skin toxicity, Neuropsychiatric toxicity, and infection) on common steroid-related adverse events anticipated to occur in  $\geq 5\%$  of patients treated in a clinical trial involving glucocorticoids. Note that for this study bone mineral density was not collected, and therefore not included in the derivation. The Specific List consists of 23 items (11 domains) that are mainly less common but serious adverse effects, serving as a complementary tool to the Composite GTI to ensure that all important elements of glucocorticoid toxicity were captured.

The domains of the Composite GTI and the specific list of the GTI will be assessed at Day 1, Week 13, Week 25, Week 37. The details on the derivations of baseline glucocorticoid toxicity score are provided in Appendix 2.

**Domain-specific score** for each patient at a visit is defined as the weight assigned based on the change in severity level as described for each domain in Appendix 3.

**Composite GTI score** for each patient at a visit is the sum of 8 domain-specific scores at each visit.

**Cumulative GTI score** is the sum of composite GTI score across visits. Two cumulative GTI scores, CWS and AIS, will be defined.

- **Cumulative worsening score (CWS)**

CWS is designed to assess cumulative GC toxicity, regardless of whether the toxicity has lasting effects or is transient. New toxicities that occur are added, but toxicities that

appear to resolve on follow-up are not removed. Thus, the CWS serves as a lasting record of GC toxicity observed and can only increase or remain the same over time.

CWS will be lower in the treatment arm compared to the placebo arm at the end of trial, if the treatment is effective at decreasing GC toxicity over time.

- **Aggregate improvement score (AIS)**

Patients are anticipated to have some GC toxicity at baseline, the AIS would be important in establishing that the new therapy is effective at diminishing any baseline GC toxicity over time. With the AIS, toxicities can be removed if improvement occurs, and added if worsening occurs.

AIS decrease over time means that the treatment is effective in decreasing GC toxicity level, compared to placebo which may show fluctuation of CIS over time. Negative score reflects that toxicities present at baseline (or occurring during the trial) resolved over the treatment period.

The steps to calculate the CWS and AIS at Weeks 25 and 37 are described below.

**Step 1:** Calculate domain-specific worsening score (for computing CWS in Step 2) and improvement score (for computing AIS in Step 2) at each visit.

For Domains without sub-items (Body Weight, Glucose Metabolism, Blood Pressure, Lipid Metabolism, Steroid Myopathy),

- a) For worsening score, only consider positive domain-specific score at each visit. For domain with a negative domain-specific score, the worsening score will be 0.
- b) For improvement score, all domain-specific scores (could be positive or negative) at each visit will be considered.

The Skin and Neuropsychiatric domains both have sub-items. For the Skin domain, these are Acneiform Rash, Easy Bruising, Hirsutism, Atrophy/Striae, and Erosions/tears/ulcerations. For the Neuropsychiatric domain, these are Insomnia, Depression, Mania, and Cognitive Impairment.

- a) For worsening score, only the item with the highest weight is scored for any GTI interval (typically three months) with the CWS. As an example, if neither insomnia nor depression were present at the baseline visit but there is now mild Insomnia and moderate depression present at follow-up, then only the moderate depression is scored (+63 points).
- b) For improvement score, improvement as well as worsening can be recorded. Because it is conceivable that one item might improve while another worsens, the item of greatest improvement (highest absolute weight) and the item of greatest worsening (highest weight) are recorded for given GTI interval.

For Infection Domain, the worsening score and improvement score handle the scoring of infections differently, because the CWS and AIS reflect reciprocal measures of GC toxicity.

- a) For worsening score, the most severe infection in every GTI interval is scored.
- b) For improvement score, only the most severe infection occurring among Week 13, Week 25, and Week 37 is scored.

**Step 2:** Calculate composite worsening score and improvement score at each visit by summing the 8 domain-specific score.

- a) For composite worsening score, sum the 8 domain-specific worsening scores.
- b) For composite improvement score, sum the 8 domain-specific improvement scores.

**Step 3:** Calculate cumulative GTI scores by summing composite scores across visits.

- a) For CWS at Week 37, summing composite GTI worsening score at Week 13, Week 25 and Week 37.
- b) For AIS at Week 37, summing composite GTI improvement score at Week 13, Week 25 and Week 37.

The detailed information for the derivation of Glucocorticoid Toxicity Index are presented in Appendix 3.

### 6.1.11. Data Adjustments/Handling/Conventions

All p-values will be displayed in four decimals and rounded using standard scientific notation (eg, 0.XXXX). If a p-value is less than 0.0001 occurs it will be shown in tables as <0.0001.

If a patient has both non missing screening value and re screening value for a parameter, then the re screening value will be used in the analyses as the screening value.

Adverse events will be coded using the MedDRA Version 24.0.

For CS medications recorded as concomitant medications on “Other Corticosteroid Concomitant Medications” eCRF form, partial end date recorded will be imputed to a date as late as possible based on the available partial date information, but no later than the date of last dose of study drug. This date imputation will be applied prior to implementation of the imputation method described in Section 6.1.5.2.

Other than the above CS dose end date imputation, no actual imputation of other medication start/end dates will be performed. If a medication start date or end date is missing or partially missing, and available information is not enough to determine whether CM was taken prior to first dose of study drug or only concomitantly with study drug, the CM will assumed to be both a prior and concomitant medication, and across as many treatment period as possible based on the available information. These data imputations are for categorization purpose only and will not be used in listings.

Missing or partial AE onset dates will be imputed so that if the partial date information is not sufficient enough to determine whether or not the AE started prior to first dose of study drug, the AE will be classified as treatment-emergent. However, if the question “Did this AE occur before the first dose of study drug?” in the AE eCRF form has the answer of “Yes”, then the AE will be counted as pre-treatment AE instead of TEAE. If the partial date information is not sufficient enough to determine during which period the AE started, the AE will be counted in the earlier period. These data imputations are for categorization purpose only and will not be used in listings. No imputation is planned for date of adverse event resolution.

## **7. Study Patients/Subjects and Demographics**

### **7.1. Disposition of Patients/Subjects and Withdrawals**

The number and percentage of subjects randomized, completing, and withdrawing, along with reasons for withdrawal, and included in each population will be tabulated overall and by treatment group. The number of screened subjects will also be reported. This summary will be presented by trial Phase (Blinded Treatment Period, Open-Label Extension Period, and Long Term Extension separately). A summary of the number of patients enrolled, randomized, and treated at each site will also be produced.

Disposition and analysis population data will be listed. A listing of randomization codes and treatment values will also be provided.

### **7.2. Protocol Violations and Deviations**

Protocol violations will be identified and finalized prior to database lock. The number and percentage of subjects with any important protocol deviations will be tabulated by treatment group and overall for the mITT population. Important protocol deviations will be further broken down by category. Subjects with one or more important deviations within each category will only be counted once.

All protocol deviations will be listed.

### **7.3. Demographics and Other Baseline Characteristics**

Demographic and baseline characteristics variables will include age, sex, ethnicity, race, BMI, disease category, disease status (newly diagnosed/relapsing), Total PDAI Activity score, Total PDAI Activity Score category (<15, 15-45, ≥46), Total Anti-DSG1, Total Anti-DSG1 category (<100, ≥100), Total Anti-DSG, Total Anti-DSG category (<100, ≥100), and time since Pemphigus diagnosis (years). Summary statistics for demographic and baseline characteristics will be presented separately by treatment group as well as overall.

For the continuous variables, the number of non-missing values and the mean, standard deviation, minimum, median and maximum will be tabulated.

For the categorical variables, the counts and proportions of each value will be tabulated.

The number and percentage of subjects reporting various medical histories, grouped by MedDRA system organ class and preferred term (coded using MedDRA v24.0), will be tabulated by treatment group. Pemphigus procedure history will be presented separately from non-pemphigus medical history.

These analyses will be conducted for ITT population.

## 7.4. Exposure and Compliance

The following parameters will be summarized by treatment group for the safety population, and for blinded treatment period and open-label extension period:

- Treatment exposure
- Study drug compliance
- Corticosteroid compliance
- Number of times that CS was not returned during blinded and open-label periods,

Study exposure will also be summarized for long term extension period.

For subjects who are missing the date of last study drug administration, for any reason, the last study visit date will be used in the calculation of treatment duration, and exposure will be calculated up to that date. Study drug compliance will not be calculated for those subjects whose date of last study drug administration is unknown. The number and percentage of patients with compliance between 80% and 125% will be tabulated for both study drug and CS.

The compliance for CS is based on systemic prescription doses collected on “Prednisone/Prenisoline Accountability” eCRF form. CS doses collected as concomitant medications on “Other Corticosteroid Concomitant Medications” eCRF form are not included in the compliance calculations.

For the blinded period, CS doses collected from Day 1 until Week 37 Visit (until early termination visit for patients prematurely discontinued study prior to Week 37 visit) are included in the derivation. For open label extension period, CS doses collected from beginning of open label extension period until Week 61 Visit (until early termination visit for patients prematurely discontinued study during the open label extension period) are included in the derivation. For long term extension period, CS doses collected from beginning of long term extension period until Week 109 Visit (until early termination visit for patients prematurely discontinued study during the open label extension period) are included in the derivation.

## 8. Efficacy Analysis

A summary of the study endpoints and their corresponding analysis methods are presented in [Table 6](#). Further details of each analysis are presented in the following sections.

**Table 6: Efficacy Endpoints and Analysis Methods**

	Endpoint	Analysis Method
Primary	Proportion of patients who are in CR from Week 29 to Week 37 with a CS dose of $\leq 10$ mg/day	Cochran-Mantel-Haenszel test stratified by disease history (newly diagnosed or relapsing).
Secondary Endpoints (in hierarchy)	Cumulative CS dose from Baseline to Week 37	Analysis of covariance, with CS dose duration (in days) during the blinded treatment period time to study discontinuation as the covariate, with terms for treatment group, and disease history.
	Cumulative duration of CR with CS dose $\leq 10$ mg/day from Baseline to Week 37 (days)	Zero-inflated negative binomial with terms for treatment group and disease history with an offset term based on the number of days on study during the Blinded Treatment Period
	Time (Days) to first CR with a dose of $\leq 10$ mg/day from Baseline to Week 37	Log rank test stratified by disease history
	Proportion of patients with at least one disease flare/relapse from initial control of disease activity (CDA) to Week 37	Cochran-Mantel-Haenszel test stratified by disease history
	Cumulative duration of CR with CS dose $\leq 10$ mg/day from Week 37 to Week 61 (days)	Zero-inflated negative binomial with terms for treatment group and disease history with an offset term based on the number of days on study during the Blinded and unblinded Treatment Period
	Cumulative duration of CR with CS dose = 0 mg/day from Week 37 to Week 61 (days)	Zero-inflated negative binomial with terms for treatment group and disease history with an offset term based on the number of days on study during the Blinded and unblinded Treatment Period

	Endpoint	Analysis Method
Secondary Endpoints (not in hierarchy, family-wise error rate not controlled)	The proportion of patients who are in CR from Week 29 to Week 37 with a CS dose of $\leq 5$ mg/day	Cochran-Mantel-Haenszel test stratified by disease history
	The proportion of patients who have PDAI score $< 3$ from Week 29 to Week 37 with CS $\leq 10$ mg/day	Cochran-Mantel-Haenszel test stratified by disease history
	Cumulative duration of CR with a CS dose of $\leq 10$ mg/day (days) from Baseline to Week 61	Zero-inflated negative binomial with terms for treatment group and disease history with an offset term based on the number of days on study during the Open-Label Extension Period
	Cumulative duration of CR with a CS dose = 0 mg/day (days) from Baseline to Week 61	Zero-inflated negative binomial with terms for treatment group and disease history with an offset term based on the number of days on study during the Open-Label Extension Period
	GTI scores at Week 37	Analysis of covariance, with treatment, disease history as fixed effects, and baseline GTI score, baseline CS dose as covariates
	Change from Baseline in PDAI Score at Weeks 5, 13, 25, 37, and 61	MMRM with terms for treatment, week, baseline score, disease history, and treatment by week interaction
	Change from Baseline in ABQOL Score at Weeks 5, 13, 25, 37, and 61	MMRM with terms for treatment, week, baseline score, disease history, and treatment by week interaction
	Proportion of patients with ABQOL Score of zero at Weeks 5, 13, 25, 37, and 61	Cochran-Mantel-Haenszel test stratified by disease history at each visit
	Change from Baseline in EQ-5D-5L visual analog scale [VAS] results and individual dimension score categories at Weeks 5, 13, 25, 37 and 61	Continuous outcomes: MMRM with terms for treatment, week, baseline score, disease history, and treatment by week interaction. Categorical outcomes: Cochran-Mantel-Haenszel test stratified by disease history

	Endpoint	Analysis Method
	Time to first flare/relapse from initial CDA to Week 37	Log rank test stratified by disease history
	Time to first CR with a CS dose $\leq$ 10mg/day, from Baseline to Week 61	Log rank test stratified by disease history
	Proportion of patients with 3 or more lesions within 1 month or extension of established lesions that do not heal spontaneously within 1 week from Baseline to Week 37	Cochran-Mantel-Haenszel test stratified by disease history
	Total number of disease flares/relapses from initial CDA to Week 37	Zero-inflated negative binomial with terms for treatment group and disease history with an offset term based on the number of days on Post initial CDA

To ensure the overall type I error rate of  $\alpha = 0.05$  will be maintained for the study, hierarchical testing, based on a fixed sequence procedure, will be used for the primary endpoint and continuing for the key secondary endpoints. The CMH primary analysis, as described in Section 8.1, will be the starting point for the hierarchical testing. If statistical significance is declared for the primary analysis, formal hypothesis testing will continue for the key secondary endpoints in sequence (see Section 6.1.3 for sequence of testing) until a non-significant result is reached. All other p-values from secondary and exploratory endpoints, after a non-significant p-value is reached, will be considered nominal. All statistical tests will be performed using two-tailed tests.

For Cochran-Mantel-Haensel tests, if stratum cell sizes are too small based on the Mantel-Fleiss criterion (Mantel, 1980) a Pearson Chi-square test will be used instead without stratification for disease history. If expected cell counts for the unstratified test are less than 5, a Fisher's Exact test will be used.

Analysis of covariance model residuals for the key secondary endpoint evaluated graphically for normality (e.g. quantile-quantile plot) and variance homogeneity (residual plots); additionally, a Kolmogorov-Smirnov test will be performed. A non-parametric will be considered appropriate if the two-sided p-value for the test is significant at the 0.01 level. If a parametric analysis is indicated, a rank analysis of covariance (Stokes, Davis, and Koch, 2000) will be used.

All analyses will be performed on the mITT Population as described in Section 5. Due to the small number of PF subjects expected to be enrolled in the study, the randomization strata of disease type (PV, PF) will not be included as a covariate in any of the analyses.

The analyses for efficacy endpoints involving clinical assessment CR in the blinded treatment period will be performed based on data collected on on-site visits (i.e., not including data collected from remote visits) as the primary analyses. Supportive analysis will be performed by using data collected from all visits including visits performed remotely.

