### 8.3. Other Secondary Analyses

The following endpoints will be analyzed in a manner similar to that described for the primary endpoint in Section 8.1, with exception of the additional subgroup analyses described in Section 6.1.3.2:

- The proportion of patients who are in CR from Week 29 to Week 37 with a CS dose of  $\leq 5$  mg/day
- The proportion of patients who have a PDAI score  $< 3$  from Week 29 to Week 37 with CS  $\leq 10$  mg/day

Cumulative duration of CR with a CS dose  $\leq 10$  mg/day from Baseline to Week 61; cumulative duration of CR with a zero CS dose from Baseline to Week 61 and the cumulative duration of CR with a zero CS dose from Week 37 to Week 61 will be analyzed based on the same methods described for the cumulative duration of CR with CS dose  $\leq 10$ mg/day from Baseline to Week 37.

Change from baseline to Weeks 5, 13, 25, 37, and 61 in PDAI will be analyzed using restricted maximum likelihood (REML)-based mixed model for repeated measures (MMRM) with fixed effects for treatment, week, baseline PDAI and treatment by week interaction. For the analysis of the differences at Weeks 5, 13, 25, and 37, only all data up to Week 37 will be included in the model. For the analyses of the difference at 61 weeks, only data collected during the Open-Label Extension Period will be included in the model (from Week 39 onward). A contrast will be written within the MMRM model to get each Week-specific treatment difference (least squares treatment means, treatment difference estimates and 95% CIs). ABQOL and EQ-5D-5L overall VAS scores will be analyzed similarly.

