Descriptive statistics including number, mean, SD, SE, median, minimum, and maximum will be provided by treatment group and by visit for domain-specific GTI scores, composite GTI total score, CWS and AIS. For CWS and AIS at Week 37, analysis of covariance model with treatment, disease history as fixed effects, and baseline GTI score, baseline CS dose as covariates, will be used to test the difference of the least-square means (LS means) between the treatment groups. Difference in LS means and the corresponding 95% CI along with the p-value will be provided.

Proportion of patients with at least one disease flare/relapse from initial control of disease activity (CDA) to Week 37 will be analyzed using the same methodology as the primary endpoint as described in Section 8.1.

Cumulative duration of CR with a CS dose  $\leq 10$  mg/day from Week 37 to Week 61, and cumulative duration of CR with a CS dose = 0 mg/day from Week 37 to Week 61 will be analyzed similarly to cumulative duration of CR with CS dose  $\leq 10$ mg/day from Baseline to Week 37.

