#### 8.4. Exploratory Analyses

The number and percentage of patients with relapse after achievement of CR through Week 61 (Yes/No) will be presented by treatment group. A similar summary will be presented for patients that reached CR with a zero CS dose by from Week 53 to Week 61 (Yes/No).

Observed values and changes from Baseline in Treatment of Autoimmune Bullous Disease Quality of Life (TABQOL) will be presented at each study visit based on summary statistics by treatment group. Descriptive summaries for the Open-Label and Long Term Extension periods will report data by treatment group in double-blinded portion and overall.

The total number of disease flares/relapses from initial Week 37 to Week 61 will be analyzed based on the same methodology described for the cumulative duration of CR with CS dose  $\leq 10$ mg/day from Baseline to Week 37 in Section 8.2, using an offset term representing the time of patient participation in the Open-Label Treatment Period.

During the COVID-19 pandemic, measures to ensure continued drug supply and safety monitoring for patients were implemented. In-clinic study visits, as outlined in the protocol schedule of assessments, may be changed to a remote visit (e.g., telephone call, video call) as needed to address the COVID-19 restrictions. As a result, statistical analyses of efficacy endpoints involving CR assessment for the blinded treatment period will not include data collected from these remote visits. The incidence of remote visits and the corresponding reason for missing the onsite visits will be summarized by visit. Supportive analysis will be performed by including data collected remotely.

The analyses of the following endpoints will be documented and reported separately:

- Exploratory PK/PD analysis will examine the effects, if any, of covariates on PK and/or PD, and the relationship between PK, PD and efficacy in this population
- Cost utilities based on the number and type of hospitalizations, outpatient medical visits, concomitant medication use, adverse events and other relevant outcomes
- the temporal relationship of change in PDAI with changes in quality of life and health economic variables.

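### SAP Table 6 crosses the exposure offsets of four other secondary CR-duration models; a rise in false rejection is shown only for the ≤10 mg/day Baseline-to-Week-61 model, and only with very early open-label exits

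*SAP*

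**What the plan says.** SAP Section 8, Table 6, plans a zero-inflated negative binomial model with treatment and disease history for each cumulative CR duration, plus an offset:

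- Baseline to Week 37, CS ≤10 mg/day: "offset term based on the number of days on study during the Blinded Treatment Period".
- Week 37 to Week 61, CS ≤10 mg/day and CS = 0 mg/day: "offset term based on the number of days on study during the Blinded and unblinded Treatment Period".
- Baseline to Week 61, CS ≤10 mg/day and CS = 0 mg/day: "offset term based on the number of days on study during the Open-Label Extension Period".

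Section 8 introduces the table with the statement "Further details of each analysis are presented in the following sections". Section 8.2 describes the Baseline-to-Week-37 model but names no offset. Section 8.3 says that both Baseline-to-Week-61 durations and the 0 mg/day Week-37-to-61 duration "will be analyzed based on the same methods described for the cumulative duration of CR" from Baseline to Week 37. It closes by saying that both Week-37-to-61 durations "will be analyzed similarly to cumulative duration of CR with CS dose" over that same first window. Section 8.4 does name an offset for flares from Week 37 to Week 61: "using an offset term representing the time of patient participation in the Open-Label Treatment Period".

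On the analysis set, Section 8 states: "All analyses will be performed on the mITT Population as described in Section 5". SAP 2.3.2.3 lists all four durations as other secondary endpoints, and SAP 6.1.4 treats everything outside the primary and key secondary sequence as exploratory and unadjusted.

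**The concern.** An offset should measure the time over which the events were counted. Here a count over up to 420 planned days is divided by up to 168 days, and a count over up to 168 days by up to 420. If every patient completes, the error is a constant and cancels from the treatment comparison. It matters once patients leave.

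Two consequences are possible for Baseline to Week 61. Patients without an open-label day have no usable log offset and fall out of an analysis specified as mITT. Patients with very few open-label days carry their blinded-period CR days over a tiny denominator, so a handful of records can dominate the fit and make the model standard error too small. These models address the stated objective of longer-term durability of CR, and SAP 8.2 has p-values and confidence intervals reported for this model.

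**Working it through.** **Inputs from the documents.** Blinded period 36 weeks × 7 = 252 days; open-label period 24 weeks × 7 = 168 days; total 420 (SAP 3.1). About 60 patients per arm (Protocol 4.1). Two-sided 0.05 (SAP 4.1). The tested quantity is the treatment coefficient in the negative binomial part (SAP 8.2). The plan states no error rate or power for these models, so there is no figure to reproduce.

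**Assumed.** The log(days) form, the dropout rates and timing, and the CR rates. The public text gives none of them.

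**Why timing decides the size.** Take a patient who leaves on open-label day d, with a constant CR rate over both periods. The Table 6 rate relative to a completer's is

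[(252 + d)/d] ÷ [420/168] = (252 + d)/(2.5 d).

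- d = 1: 253/2.5 = 101.2-fold
- d = 14: 266/35 = 7.6-fold
- d = 28: 280/70 = 4.0-fold
- d = 84: 336/210 = 1.6-fold
- d = 168: 1

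With the matched offset the factor is 1 for every d.

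**Null simulations, CS ≤10 mg/day, Baseline to Week 61.** True ratio 1.00, 60 per arm, equal open-label dropout, Wald test at 0.05. Generator A is zero-inflated negative binomial on total days (dispersion 0.5, 30% structural zeros). Generator B has remission onset and relapse bounded by follow-up, with 30% never in CR. There were 1,500–2,000 runs per cell. Monte Carlo error near 5% is √(0.05 × 0.95/2000) = 0.5 points. False rejection with the Table 6 offset:

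| Exit pattern | Dropout | A | B |
|---|---|---|---|
| None | 0% | 5.9% | 1.9% |
| Uniform from day 1 | 5 / 10 / 20 / 30% | 14.8 / 20.3 / 25.4 / 29.6% | 9.6 / 13.0 / 20.7 / 25.6% |
| At scheduled visits (first at day 14) | 5 / 10 / 20 / 30% | 11.1 / 12.9 / 15.5 / 17.7% | 4.3 / 7.1 / 11.0 / 11.0% |
| From day 28 | 5 / 10 / 20 / 30% | 5.8 / 7.2 / 7.6 / 8.1% | 2.6 / 2.7 / 2.7 / 3.5% |
| From day 84 | over the range | 5.7–6.4% | 2.0–2.2% |

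The matched offset stays at 4.8–6.8% (A) and 1.5–2.8% (B) throughout. Two further implementations at 5% dropout uniform from day 1 give 14.1% against 5.0% matched (2,000 runs) and 10.8% against 4.6% (500 runs; error √(0.11 × 0.89/500) = 1.4 points).

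**Ratio, same row** (2,000 runs; drug vs placebo dropout; truth 1.00).

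- 10% vs 25% before Week 37 only: 1.00, rejection 5.9%.
- The same plus 5% vs 15% open-label: 0.88, rejection 21.1% (6.4% matched).
- Response-related dropout before Week 37 (40% among placebo patients with a below-median CR rate, 10% otherwise): 0.90, rejection 10.1% (matched 0.99 and 6.6%).

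**CS = 0 mg/day, Baseline to Week 61.** SAP 6.1.9 holds CS at 5 mg until Week 37, so days at 0 mg hardly accrue earlier and open-label days are close to the right exposure. With 0 mg days starting only after a 1 mg/week taper from Week 37, rejection is 0.9–1.4% with Table 6 and 0.9–1.5% matched at 0–30% dropout. The 500-run check gives 7.2% for both at 5%.

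**Week 37 to 61.** For CS ≤10 mg/day with equal dropout, rejection under Table 6 is 4.5–6.2% (A) and 1.0–1.9% (B). Across a wider set of dropout scenarios the ratio is 0.99–1.06 and rejection 4.8–7.5%. The exception is response-related dropout (0.91, 8.9%), where the matched offset does no better (0.90, 9.8%).

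**Exclusions.** If 20% leave before Week 37, 0.20 × 60 = 12 patients per arm have no open-label day and drop out of both Baseline-to-Week-61 models.

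**The case against.** The best defence is that these are probably transposed cells, in endpoints that the protocol (9.3.6, other secondary) analyses mainly descriptively and that SAP 6.1.4 leaves unadjusted. That limits the importance but leaves the text wrong.

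The defence on timing largely stands. The documents give no dropout rate or timing, and the rise needs very early exits. Under generator B, 5% leaving at scheduled visits gives 4.3%, below nominal. Early leavers are asked back four weeks after their last dose (Protocol 4.4). If that follow-up counts as days on study, near-zero offsets become less likely; the SAP does not say. Early exit remains possible: need for rituximab in the open-label period forces discontinuation (SAP 3.1), and patients who withdraw consent have no further visits (Protocol 7.2.2).

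Three stronger readings are tempting. A reader might infer that any open-label dropout inflates the error, or that all four models suffer; the day-28 and day-84 results, the 5 mg hold and the Week-37-to-61 results contradict both. A reader might read Section 8.3 as replacing the Table 6 offsets with blinded days. That is strained, because the table gives these rows offsets of their own, and blinded days would fit neither window. A reader might also assume a substitute value for zero days. The public text has none and parts of the SAP are withheld, so no size can be attached to such a rule.

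An arm difference in open-label dropout is likewise only an assumption, since both arms take active drug from Week 37.

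**Conclusion.** The crossing is certain from the printed table, departs from the SAP's own practice, and is not repaired in Sections 8.2 or 8.3. Under a log(days) offset, both Baseline-to-Week-61 models lose patients with no open-label day.

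A rise in false rejection is shown for one model only: CS ≤10 mg/day, Baseline to Week 61. It is about 11–15% against about 5% at 5% equal dropout with exits uniform from day 1 under the zero-inflated negative binomial generator, and 9.6% against 1.9% without dropout under the bounded-remission generator. It shrinks quickly as first exits move later. That model's ratio can also be biased if open-label dropout differs by arm, or if dropout before Week 37 is related to response. All sizes rest on assumed dropout and CR rates.

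A reader might infer a threat to the trial's type I error. The documents do not support that: the primary and three key secondary endpoints do not use these offsets, and the four p-values are nominal. This is a minor correction to other secondary analyses.

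**What to change.** In SAP Table 6:

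- For both Baseline-to-Week-61 durations, set the offset to log(days on study from Day 1 to Week 61). Every mITT patient has at least one such day and stays in. For the CS = 0 mg/day row the gain is window consistency and retention of mITT, not error control; patients leaving before Week 37 then contribute almost no CR days with positive exposure, which should be acknowledged.
- For both Week-37-to-61 durations, set the offset to log(open-label days on study), as Section 8.4 already does for flares. Only patients with at least one open-label day can enter, which is a post-randomisation subset. Report the number excluded by arm and interpret accordingly; the matched offset does not remove that selection.
- State the log form, the zero-day rule, and whether follow-up after the last dose counts as days on study.
- Point both Section 8.3 statements to these offsets.

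Editorially, move the three rows that SAP version 3 reclassified out of the hierarchical block of Table 6, to agree with SAP 2.2 and 6.1.4.

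The cost is four table cells, the Section 8.3 cross-references, a short rule and the program specification. No data or design changes.
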